3.4. Clinical Trial Duration for Individual Subjects

The clinical trial consists of 10 clinic visits over a period of approximately 16 weeks.

3.5. Clinical Trial Population Selection

The intended population will be adult subjects with retinitis pigmentosa due to rhodopsin mutations (including P23H) will be identified and treated with serial intravitreal injections of ADX-2191 in the worse seeing eye.

3.5.1. Inclusion Criteria

Subjects meeting **ALL** of the following criteria will be considered eligible for clinical trial entry:

1. Subjects age 18 or older of any gender
2. Diagnosis of retinitis pigmentosa due to rhodopsin gene mutation, including P23H, confirmed previously by a CLIA or an investigational/academic lab
3. Impairment on VF in the opinion of the Investigator, as determined by perimetry
4. Willing to participate in the study as evidenced by signing of an informed consent document
5. Subjects of childbearing potential, both male and female, must agree to use two forms of birth control for the duration of the clinical trial. Males should continue to use the two forms of birth control for a minimum of three months after last injection. Females

of childbearing potential must use the two forms of birth control for a minimum of 30 days following their last injection

6. For females of child-bearing potential, subjects must have a negative pregnancy test at Screening and not lactating

3.5.2. Exclusion Criteria

Subjects meeting ANY of the following criteria will be excluded from the clinical trial:

1. Known allergy or hypersensitivity to methotrexate
2. BCVA worse than LogMAR BCVA 1.0 (Snellen equivalent 20/200) in the worse seeing eye
3. History of severe dry eye, corneal herpetic disease, LASIK, penetrating keratoplasty, or other significant corneal disease
4. Inability or unwillingness to use artificial tears during the study period
5. Pre-existing eye conditions or complicating systemic diseases that could interfere with the interpretation of the study or create inconsistent follow up. Examples may include severe cardiovascular disease, malignancy, diabetes or sickle cell disease if manifestation of advanced retinopathy is present, or subjects with immunodeficiency
6. Planned eye surgery during the study period
7. Participation in any clinical study of an investigational product within 90 days prior to enrollment
8. Have previously received Methotrexate (intravitreally, systemically, or any other route) within 3 months of Screening Visit A (V1)
9. Patients who may need to use Methotrexate for another medical condition during the study period
10. Any history of systemic or ophthalmic condition or circumstances which, in the opinion of the Investigator, could compromise the subject's ability to comply with the protocol or that could compromise the subject's safety or the interpretation of the clinical trial results

3.6. Strategies for Recruitment and Retention

Subjects will be recruited directly from the investigative sites' patient population or will be referred for treatment by other physicians. Once enrolled, subjects will be provided with the visit schedule and reminders from the clinical trial staff in advance of their visits to assist with compliance to the schedule of events for the clinical trial.

Subjects who discontinue early from investigational product treatment will complete the end-of-study visit (Week 16) at time of discontinuation. The Sponsor and Investigator will make all efforts to retain all subjects in the clinical trial until the end-of-study visit (Week 16) and to follow-up with early-discontinued subjects for safety purposes.

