4.3. Subject Withdrawal

Subjects will be removed from the clinical trial if they develop infectious endophthalmitis and/or no light perception vision. Subjects may also be removed at the discretion of the principal investigator or at the wishes of the subject himself/herself.

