4.4. Handling of Subject Withdrawals or Subject Discontinuation of Clinical Trial Intervention

Subjects that are dropped from the clinical trial prior to administration of the interventional investigational product will be considered screen failures and will not be included in analysis.

Any subject receiving the investigational product will be followed for safety throughout the scheduled course of the clinical trial, or until the subject has reached a status of un-reachable. To assure the clinical trial meets the required approximate 8 evaluable eyes for analysis, additional subjects may need to be enrolled to meet this goal.

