6.6. Urine pregnancy testing

For women of childbearing potential (WOCBP), a urine pregnancy test will be collected at the Screening Visit B (Visit 2), and prior to each injection of ADX-2191, through Visit 8 / Week 10. Results must be available and confirmed to be negative before the subject may be enrolled in the clinical trial. IP must be discontinued for any subject with a positive pregnancy test result.

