6.7.4. Full Field Electroretinography

A standard full-field electroretinogram (ERG) will be performed. Change in dark-adapted flash (0.01 cd•s•m⁻²) b-wave amplitudes will be analyzed. Testing will be performed using a standard

International Society for Clinical Electrophysiology of Vision (ISCEV) protocol. Both eyes will be evaluated. ERG will be collected at Visits V1 and V9.

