7.9. Week 12 (Visit 9)

- Perform BCVA (Section 6.7.1)
- Perform LLVA (Section 6.7.2)
- Perform Full Ophthalmic Examination (Section 6.7.7)
- Collect Wide Field Color and Autofluorescence Fundus Photographs (Section 6.7.8)
- Collect Macular Optical Coherence Tomography (Section 6.7.6)
- Collect Dark-Adapted Chromatic Perimetry (Section 6.7.5)
- Collect Macular Integrity Assessment (MAIA) (Section 6.7.3)
- Collect concomitant medications (Section 6.4)
- Collect adverse events (Section 6.5)
- Collect Full-field electroretinography (ERG) (Section 6.7.4)

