8.7. Reporting Pregnancies

Pregnancies for women will be reported from the time the subject signs the informed consent form through final clinical trial visit or 30 days after the last IP administration, whichever is later. Males will report pregnancy of their partners through 90 days after the last IP administration.

Subjects who become pregnant will be withdrawn from the clinical trial. The pregnancy should be followed up to determine outcome, including spontaneous or voluntary termination, details of the birth, and the presence or absence of any birth defects, congenital abnormalities, or maternal and/or newborn complications.

Pregnancy should be recorded on a subject's source documents and a Pregnancy Notification and Outcome Form and reported using the same procedure for reporting SAEs detailed in Section 8.6.2. A pregnancy, by itself, is not an SAE. Pregnancy follow-up should also be recorded and should include an assessment of the possible relationship to the IP of any pregnancy outcome. Any pregnancy-related SAE (e.g., spontaneous abortion, birth defect) or any other SAE experienced during pregnancy must be recorded on a separate SAE Report Form and reported per SAE reporting procedures in Section 8.6.2.

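### For subjects who stop product early, the protocol secures neither the only post-baseline ERG nor visual function measured at the true Week 16

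*Combined protocol and SAP*

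**What the plan says.** Section 3.6 sets the rule for early stoppers: "Subjects who discontinue early from investigational product treatment will complete the end-of-study visit (Week 16) at time of discontinuation". Its next sentence gives a general aim of retaining everyone to the Week 16 visit. For those who stopped, it adds an effort "to follow-up with early-discontinued subjects for safety purposes". Section 3.1 says that all subjects are followed for 16 weeks. Section 4.4 is firmer, but limited to safety: "Any subject receiving the investigational product will be followed for safety throughout the scheduled course of the clinical trial".

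Section 9.2.5 lists the safety endpoints as slit-lamp evaluation, dilated ophthalmoscopy and adverse event query. BCVA, LLVA, MAIA, DAC perimetry and ERG are secondary endpoints (Section 2.2.2).

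On ERG timing, Section 6.7.4 says "ERG will be collected at Visits V1 and V9". Table 1 agrees, and the Week 16 list in Section 7.10 has no ERG. Section 9.2.6 analyses secondary endpoints as change from Visit 2 to Week 16, which it identifies as Visit 10. Section 9.2.2 leaves missing-data rules to the SAP and mentions only adverse events and medications. Under Section 9.2.8 the SAP is finalised before database lock; the supplied file contains no separate SAP text.

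**The concern.** Stopping product and ending study assessments are different events, and Section 3.6 runs them together. A site that follows it would do the Week 16 procedures when product stops and then continue for safety only. Two things would be left open.

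- **Data.** The V9 ERG and the functional tests at the true Week 16 might never be collected in a subject who stopped. No later analysis document can recover them.
- **Label.** A visit held weeks early has the same name as the visit that Section 9.2.6 analyses.

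Subjects who stop treatment are often those whose later course matters most. With four subjects per cohort, one such case carries a large share of any cohort mean.

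**Working it through.** The plan gives no figure to reproduce here: it states no stopping rate, effect size or standard deviation. The check is visit arithmetic from Table 1 and Sections 6.7.4, 7.9 and 7.10.

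**Inputs.** Week 0 is Day 0 and Week 16 is Day 112. Injections are at Weeks 0, 4 and 8 in Cohort A, and at Weeks 0, 2, 4, 6, 8 and 10 in Cohort B. Windows are ±3 days at Weeks 2 and 4, and ±5 days from Week 6 to Week 16. The earliest in-window V10 is therefore Day 112 − 5 = 107.

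**How early the exit visit falls.** Assume that product is stopped at a scheduled injection visit after the first and that the exit assessment is done that day. The nominal gap is 112 − (7 × week). The smallest in-window gap is 107 − (7 × week + window).

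| Stop at | Cohort | Nominal gap | Smallest in-window gap |
|---|---|---|---|
| Week 2 (V4) | B | 112 − 14 = 98 days (14 weeks) | 107 − 17 = 90 days |
| Week 4 (V5) | A, B | 112 − 28 = 84 days (12 weeks) | 107 − 31 = 76 days |
| Week 6 (V6) | B | 112 − 42 = 70 days (10 weeks) | 107 − 47 = 60 days |
| Week 8 (V7) | A, B | 112 − 56 = 56 days (8 weeks) | 107 − 61 = 46 days |
| Week 10 (V8) | B | 112 − 70 = 42 days (6 weeks) | 107 − 75 = 32 days |

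The nominal range is 8 to 12 weeks in Cohort A and 6 to 14 weeks in Cohort B. A stop declared some time after the missed dose would shorten the gap. In every row the exit visit lies well outside the ±5-day window for V10.

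**Whether the ERG could already have been done.** The latest V8 is Day 75 and the earliest V9 is Day 84 − 5 = 79, so the last injection visit is at least 79 − 75 = 4 days before V9. A subject who stops at any scheduled injection visit has therefore not had the V9 ERG. Because the Week 16 list contains no ERG, the one post-baseline ERG out of one is not secured.

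**Weight of one subject.** Without replacement: 1/8 = 12.5% overall and 1/4 = 25% of a cohort. Section 4.4 allows further enrolment, and Section 9.1.1 keeps the stopped subject in the ITT population. With one replacement the shares are 1/9 = 11.1% and 1/5 = 20%.

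**The case against.** The strongest reply is that the protocol does intend full follow-up. Section 3.1 follows all subjects for 16 weeks, Section 3.6 aims to retain everyone to Week 16, and Section 4.4 runs over the scheduled course. For safety this stands: adverse event, slit-lamp and dilated-exam follow-up is reasonably protected. A reader might infer that safety examinations are lost once the exit visit is done, but that would mean disregarding Section 4.4. For function the reply falls short. The 3.1 and 3.6 statements are general, whereas the specific rule has already used up the end-of-study visit of an early stopper. What continues is for safety, and Section 9.2.5 includes no functional test or ERG among the safety endpoints.

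A second reply is that the SAP can settle the label. That is right, and a visit outside the V10 window may well be read as an exit visit that merely uses the Week 16 procedures. A reader might infer that the early value will certainly be analysed as Week 16; the text does not say so either way. But a SAP cannot supply an ERG or a Week 16 test that was never done.

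Third, the exit visit does include BCVA and the other Week 16 tests, so severe loss present at the stop is recorded. That also stands; what is missing is the later measurement.

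Finally, a reader might see a conflict between Section 6.6, which stops product on a positive pregnancy test, and Section 8.7, which withdraws the subject. The two are compatible and need no alignment. After the events that trigger removal under Section 4.3 (infectious endophthalmitis or no light perception), many functional tests would be inappropriate or at floor.

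**Conclusion.** The point holds for secondary endpoints. Followed as written, Section 3.6 can lose the only post-baseline ERG in a subject who stops product. It leaves BCVA, LLVA, MAIA and DAC perimetry secured only at a visit nominally 6 to 14 weeks before the true Week 16, and never less than 32 days before it when the stop is at a scheduled injection visit within its window. Whether that visit counts as Visit 10 in Section 9.2.6 is unstated.

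The size is one subject's weight: 12.5% overall and 25% of a cohort, or 11.1% and 20% with one replacement. The documents give no probability of early stopping. The direction of bias cannot be stated either, because an early value may miss later harm, recovery or benefit. The primary endpoint is safety and tolerability, and it is not undermined. This is a worthwhile, low-cost improvement.

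**What to change.** 1. In Section 3.6, state that stopping product is not leaving the trial. Dosed subjects stay on the original calendar through V9 (including ERG) and V10, unless they withdraw consent or a test is clinically inappropriate. The stopping and withdrawal criteria in Sections 4.3, 6.6 and 8.7 can stand.
2. Record the assessment at discontinuation as Early Termination on its actual study day, not as Visit 10. Do the ERG at that assessment only if the subject will not return for V9.
3. In Section 9.2.6, use actual Week 16 values (Week 12 for ERG, which is not scheduled at Week 16). For subjects without one, list the early-termination value and repeat the summary with it included, so that an eye with severe loss is not dropped.

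The cost is protocol wording, a few already-planned visits kept for subjects who stop early, and at most one ERG per early leaver moved to the exit assessment.

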4. SUBJECT DISPOSITION

4.1. Completed Subjects

A completed subject is one who has not been discontinued from the clinical trial.

4.2. Discontinued Subjects

Subjects may be discontinued prior to their completion of the clinical trial due to:

- Subject request/withdrawal
- AEs
- Positive pregnancy results
- Protocol violations
- Administrative reasons (e.g., inability to continue, lost to follow-up)
- Sponsor termination of the clinical trial
- Any sound medical reason, as determined by the investigator
- Others

Notification of a subject discontinuation and the reason for discontinuation will be made to the Sponsor or designee and will be clearly documented on the CRF.

4.3. Subject Withdrawal

Subjects will be removed from the clinical trial if they develop infectious endophthalmitis and/or no light perception vision. Subjects may also be removed at the discretion of the principal investigator or at the wishes of the subject himself/herself.

4.4. Handling of Subject Withdrawals or Subject Discontinuation of Clinical Trial Intervention

Subjects that are dropped from the clinical trial prior to administration of the interventional investigational product will be considered screen failures and will not be included in analysis.

Any subject receiving the investigational product will be followed for safety throughout the scheduled course of the clinical trial, or until the subject has reached a status of un-reachable. To assure the clinical trial meets the required approximate 8 evaluable eyes for analysis, additional subjects may need to be enrolled to meet this goal.

4.5. Premature Termination or Suspension of Clinical Trial

In the event of premature termination or suspension of clinical trial, the subject will continue to follow with his/her physician as part of their usual standard of care.

5. INVESTIGATIONAL TREATMENT

Product Name: ADX-2191 (methotrexate 0.8%) for intravitreal injection.

5.1. Description of Investigational Product

Methotrexate is an antimetabolite and antifolate drug that has been used for cancer treatment since the 1950s. The drug was originally approved in 1959 and is now available generically. It has exceptionally well-understood biological and clinical effects. Methotrexate is currently FDA-approved for oral administration and for intravenous, intramuscular, intrathecal, or intra-arterial injection. Approved indications include psoriasis, rheumatoid arthritis, and certain neoplastic diseases. Other mechanisms of action involve direct effects on inflammatory pathways, in particular neutralization of the effects of TNF- α and IL-1 β , though the molecular mechanisms underlying these effects remain largely uncharacterized.

Several case series have been published using intravitreal injections of methotrexate, most commonly for intraocular lymphoma. (Frenkel et al., 2008; Hardwig, Pulido, & Bakri, 2008; Hardwig, Pulido, Erie, Baratz, & Buettner, 2006; Samson, Waheed, Baltatzis, & Foster, 2001)

5.2. Packaging and Labeling

ADX-2191 drug product is formulated as a sterile and aqueous solution for intravitreal delivery. The drug product will be supplied in single-dose, 2 mL glass vials with a 0.5 mL fill volume.

The ADX-2191 drug product is formulated in 7.5% sucrose and phosphate buffered at pH 7-8.

The quantitative composition of the ADX-2191 drug product are presented in [Table 2](#).

Table 2: Composition of ADX-2191 Drug Product

Component	Amount (%w/v)	Grade
ADX-2191 (methotrexate)	0.8%	GMP
Sucrose	7.5%	USP/NF
Sodium Phosphate Dibasic	0.114%	USP
Sodium Hydroxide or Hydrochloric Acid	pH adjustment	USP/NF
Sterile Water for Injection (WFI)	Dilute to volume	USP

5.3. Investigational Product Storage

ADX-2191 drug product (0.8% Methotrexate Solution for Intravitreal Injection) will be supplied to the clinical sites in a clear 2 mL vial as an aqueous solution that does not require reconstitution. ADX-2191 must be stored at 2 to 8°C (36 to 46°F) in an upright position. Do not freeze. Protect from light while in storage (this does not apply to time of preparation and administration).

The Investigational Product (IP) must be stored in a secure area accessible only to the investigator and his/her designees. The IP will be administered only to subjects entered into the clinical trial, in accordance with the conditions specified herein.

The subject kit label will include, but not limited to, the following information:

- trial protocol number
- contents
- subject number and initials (manually recorded)
- storage conditions
- Investigational New Drug statement
- Sponsor's name, address, and phone number

The vial label will be included, but not limited to, the following information:

- trial protocol number
- contents
- storage conditions
- Investigational New Drug statement
- manufacturer name and address
- Sponsor name, address, and phone number

5.4. Investigational Product Dosage, Preparation, and Administration

Proposed dosage of ADX-2191: 400 µg in 0.05 mL intravitreal injection

ADX-2191 will be provided as the investigational product to clinical trial sites that have obtained IRB approval. The IP will be supplied in single-use vials. ADX-2191 should be withdrawn from the vial into an appropriate syringe allowing excess volume to accommodate needle fill if the needle will be exchanged. Used vials/syringes should be disposed of appropriately in accordance with local policy which may include use of yellow "chemo waste" bags.

Administration of ADX-2191 is described in Section 6.8. Refer to the Pharmacy Manual for additional details.

5.5. Investigational Product Accountability

The IP is to only be prescribed by the principal investigator or his/her named sub-investigator(s) and is only to be used in accordance with this protocol. The IP must be distributed only to subjects properly qualified under the conditions specified herein.

The investigator or designated qualified site staff is responsible for monitoring the inventory of IP and for the accountability of all used and unused IP received from the supplier. This includes the amount of IP dispensed to subjects, and the amount returned or disposed upon the completion of the trial. Inventories must be carefully and accurately documented according to applicable

state, federal, and local regulations, current Good Clinical Practices (GCPs), including the International Council for Harmonization (ICH) guidelines, and clinical trial procedures. IP accountability will be available for Sponsor's review and will be verified by the clinical trial monitor during site visits and at the completion of the trial.

At the conclusion of the trial, IP reconciliation will be performed, and all remaining IP not returned to the sponsor, will be destructed and disposed of according to clinical site's SOP. Sponsor will be provided with a final accounting of IP for approval prior to destruction.

The investigator or designated qualified site staff will maintain accurate records of receipt and condition of IP, including dates of receipt, and temperature log of storage conditions. In addition, accurate records will be kept of the date of IP administration and the subject to whom IP was administered. Any reasons for departure from the protocol-specified dispensing regimen must also be recorded.

5.6. Investigational Product Retention

IP must be retained until completion or termination of the clinical trial, and written authorization from the Sponsor has been received. All unused and used IP drug should be destroyed at the site or returned to the distributor, as specified by Sponsor. It is the investigator's responsibility to ensure that the Sponsor has provided written authorization prior to return or destruction, and that appropriate records of the disposal are documented and maintained. No used or unused IP may be disposed until fully accounted for by the clinical trial monitor.

5.7. Subject Compliance with Investigational Product Administration

Compliance or product administration will be assessed through accurate medication administration records maintained at the clinical sites. The investigator/or appropriately licensed designee will administer the investigational product as defined in the protocol administration schedule. IP compliance will be assessed through review of the subject's medical record.

5.8. Subject Compliance with Clinical Trial Intervention

Protocol compliance will be assessed at each clinical trial visit. Compliance information will be collected from the medical/research record and reported via an CRF. This information will be reviewed by the clinical trial monitor in accordance with the Monitoring Plan.

5.9. Assessment of Clinician and/or Subject Compliance with Clinical Trial Procedural Intervention

Clinician/subject compliance will be assessed at each clinical trial visit. Compliance information will be collected from the medical/research record and reported via a case report form. This information will be reviewed by the clinical trial monitor in accordance with the Monitoring Plan.

